9.3. Analysis of Primary Efficacy Endpoint

The primary endpoint is subjects achieving DLQI response at Week 16 (defined as ≥ 4 -point reduction in DLQI from baseline at Week 16). The primary endpoint will be analyzed using the ITT population. A supplemental analysis will be performed using the PP population.

The treatment difference in proportions of DLQI response between Apremilast 30 mg BID and placebo will be compared using CMH test adjusted for the stratification factor at randomization

Apremilast

Statistical Analysis Plan. Protocol CC-10004-PSOR-020

Amgen INC.

(i.e., the 5 difficult to treat manifestation types). This form of the CMH test will use the sample sizes in each of the strata as weights when estimating the adjusted difference in the treatment proportions, constructing 95% Wald confidence intervals for the difference, and conducting a statistical test of no difference between the treatment proportions (i.e., $H_0: \pi_{APR} - \pi_{PBO} = 0$ as the null hypothesis). The difference of the response rate (Apremilast 30 mg BID - placebo) and its 95% CI as well as the p-value will be produced using the Cochran-Mantel-Haenszel (CMH) test and adjusting for the stratification factor at randomization (i.e., the manifestations of scalp psoriasis, nail psoriasis, palmoplantar psoriasis, genital psoriasis, or psoriasis in visible locations). SAS PROC FREQ with the COMMONRISKDIFF (TEST=MH) option will be used for the analysis.

All reasonable attempts will be made to prevent missing data from occurring in the study. However, in the case of missing data at Week 16, a multiple imputation (MI) method (SAS Institute Inc. 2008) will be incorporated as the primary analysis. such that unbiased estimation and valid statistical inferences (i.e., confidence intervals and hypothesis testing) can be made.

The SAS procedure MI will be used to impute missing DLQI scores at the scheduled assessments in the Placebo-controlled Phase (Weeks 0 to 16) to create M=25 complete data sets. The missing data patterns will be checked by treatment and stratification factor at the core baseline (Week 0), Week 2, Week 4, and Week 16. If there are non-monotone missing patterns, two separate imputation procedures will be used to complete the imputation process.

In the first step, the Markov Chain Monte Carlo (MCMC) method will be used to impute missing scores by treatment and stratification factor to create M=25 imputed data sets with monotone missing patterns. The minimum and the maximum values for imputation will be 0 and 30, which correspond to the lowest and the highest DLQI scores. The seed will be set to 804529, the imputed values will be rounded to integers and a single chain will be used to produce imputations. In case there are convergence issues, the imputation will be done by treatment only. If the convergence issue remains, then the imputation will be done on data pooled from both treatment arms.

In the second step, the predictive mean matching method will be used to impute the remaining missing values for the 25 data sets with monotone missing patterns. The MONOTONE REGPMM statement will be used with seed 447159. The missing values at each visit will be imputed based on treatment, stratification factor, and DLQI scores at the core baseline and previous visits. In presence of convergence issue, a simplified regression model without stratification factor will be used. The number of closest observations to be used in the selection will be K=5.

After the completion of imputation made on the continuous-like scale of the total DLQI score, the primary endpoint will then be derived by dichotomizing the DLQI score prior to performing the CMH analysis described above. The same CMH method will be used to analyse the 25 complete data sets and the SAS procedure MIANALYZE will be used to combine the results for the statistical inferences.

In addition to the primary analysis using MI method and the supplemental analysis in PP population, the following supportive analyses using CMH method for the primary endpoint will be performed for: (1) ITT population treating missing values using the last observation carried

Apremilast

Statistical Analysis Plan. Protocol CC-10004-PSOR-020

Amgen INC.

forward (LOCF) method, (2) ITT population treating missing values using the non-responder imputation (NRI) method.

In order to assess the impact of Covid-19 on the DLQI data collection, a sensitivity analysis will be conducted by excluding the data collected via paper version of the DLQI questionnaire.

Similar analysis planned for Week 16 will be repeated for DLQI response at Week 2 and Week 4.

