4. INVESTIGATIONAL PLAN

4.1. Overall Study Design and Plan

[figure not shown]
This is a phase 4, multicenter, randomized, double-blind, placebo-controlled study of the impact of Apremilast on quality of life, efficacy, and safety in subjects with manifestations of plaque psoriasis and impaired quality of life. Approximately 276 subjects in 6-10 countries in Western Europe meeting inclusion criteria will be randomized in 2:1 ratio to receive Apremilast 30 mg BID or placebo, and to each of the stratification factors of manifestations of psoriasis (scalp psoriasis, nail psoriasis, palmoplantar psoriasis, genital psoriasis, and psoriasis in visible locations). For patients with multiple manifestations, they will be allocated to the manifestation which is most severe, as determined by the patients.

- Subjects randomized to the Apremilast treatment group will receive a 5-day titration with Apremilast followed by Apremilast 30 mg BID orally for 16 weeks. The subjects will continue with Apremilast 30 mg BID until Week 52 (i.e., a total of 52-week treatment with Apremilast). There is a dummy 5-day titration at Week 16 to maintain the blind to the original treatment assignment at randomization.
- Subjects randomized to the placebo treatment group will start with a dummy 5-day titration and receive placebo tablets (identical in appearance to the Apremilast 30 mg tablets) orally twice daily for 16 weeks. Beginning at Week 16 and after a 5-day titration with Apremilast, subjects will receive Apremilast 30 mg BID until Week 52 (i.e., a total of 36-week treatment with Apremilast).

The study consists 4 phases:

- Screening Phase – up to 5 weeks (35 days)
- Double-blind Placebo-controlled Phase – Weeks 0 through 16
Subjects will receive treatment with either
 - Apremilast 30 mg tablets orally BID, or
 - matched placebo tablets orally BID
- Apremilast Extension Phase – Weeks 16 through 52
 - All subjects will be switched to (or continue with) Apremilast 30 mg BID at Week 16 (after a 5-day titration for subjects initially randomized to placebo). All subjects will maintain this dosing through Week 52.
- Post-treatment Observational Follow-up Phase
 - 4-week post-treatment observational follow-up phase for all subjects who complete the study on treatment or discontinue from the study treatment early.

Figure 1: Overall Study Design

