4.4. Sample Size Determination

For the primary endpoint, i.e., the response rate (π) defined as the proportion of subjects achieving a ≥ 4 -point reduction from baseline in DLQI at Week 16, the superiority of Apremilast 30 mg BID versus placebo will be tested. The hypotheses on superiority are defined as:

$$H_0: \pi_{APR} - \pi_{PBO} = 0$$

versus

$$H_1: \pi_{APR} - \pi_{PBO} > 0$$

Using an exploratory analysis on a subset of subjects meeting the following criteria: a) ScPGA ≥ 3 or b) NAPSI ≥ 1 or c) PPPGA ≥ 3 at baseline and DLQI ≥ 10 at baseline in the PSOR-008 and PSOR-009 Phase 3 studies, it was estimated that the proportion of subjects who achieved a ≥ 4 -point reduction from baseline in DLQI was 0.50 (97 responders out of 193 subjects) and 0.83 (337 responders out of 406 subjects) for placebo and Apremilast 30 mg BID, respectively.

Assuming a placebo DLQI responder proportion of 0.50 at Week 16, a minimum total sample size of 210 subjects (140 allocated to Apremilast 30 mg and 70 allocated to placebo) is needed to detect a 0.20 difference in the DLQI responder rate between Apremilast and placebo with at least 0.807 power using a two-sided test at the 0.05 level of significance. This sample size calculation is based on an unpooled variance, and determined using the commercial software EaST, Version 6.3. Allowing for an 24% discontinuation rate prior to Week 16, the sample size of 276 subjects should be sufficient.

5. GENERAL STATISTICAL CONSIDERATIONS**5.1. Reporting Conventions**

- The statistical test on the primary endpoint is at a 2-sided 0.05 significance level, any p-values reported for other endpoints are considered as summary statistics;
- P-values are rounded to 4 decimal places. P-values that round to 0.0000 are presented as '<0.0001' and p-values that round to 1.000 are presented as '>0.9999';
- Confidence intervals (CIs) are presented as 2-sided 95% CIs;
- Summary statistics consist of the number and percentage of subjects in each category for discrete variables, and the sample size, mean, median, Standard Deviation (STDEV), minimum, and maximum for continuous variables;
- All mean and median values are formatted to one more decimal place than the measured value, standard deviation values are formatted to two more decimal places than the measured value, minimum and maximum values are presented to the same number of decimal places as the measured value, and the 95% CI are formatted to two more decimal places than the measured value;

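### Minor, nearly free improvement: raising the 25 imputations to 500 would remove avoidable random-number noise from the primary p-value

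*SAP*

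**What the plan says.** SAP 9.3 handles missing Week 16 DLQI by multiple imputation "to create M=25 complete data sets". An MCMC step (seed 804529) makes the missing pattern monotone. A predictive mean matching step then fills what remains: "The MONOTONE REGPMM statement will be used with seed 447159". Each completed data set is dichotomized and analysed by the stratified CMH method, and the results are pooled with PROC MIANALYZE. SAP 9.1 and 9.4.1 carry the same number, 25, over to the other imputed endpoints.

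SAP 9.2 declares apremilast effective if this two-sided p-value is below 0.05, and no secondary endpoint can be claimed unless it is. SAP 4.4 allows for 24% discontinuation before Week 16 and states that "the sample size of 276 subjects should be sufficient". The SAP gives no reason for 25, no check of Monte Carlo error and no sort order for the data entering the imputation.

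**The concern.** Multiple imputation draws random values, so the pooled estimate and its standard error vary with the seed. The variation shrinks as the number of imputations grows, but at 25 it is not negligible if about a fifth of the information is missing. It says nothing about the drug and can be almost removed by computing for longer. What is at stake is a borderline result: an analyst repeating the imputation with another seed, or with the records in another order, could land on the other side of 0.05. The whole test sequence would then stand or fall with that run.

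**Working it through.** **Inputs from the documents**

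- Two-sided alpha 0.05 and stated power: "at least 0.807 power using a two-sided test at the 0.05 level of significance" (SAP 4.4).
- Placebo rate: "Assuming a placebo DLQI responder proportion of 0.50 at Week 16" (SAP 4.4).
- Effect: "detect a 0.20 difference in the DLQI responder rate between Apremilast and placebo" (SAP 4.4), so 0.70 v 0.50.
- Evaluable subjects: "140 allocated to Apremilast 30 mg and 70 allocated to placebo" (SAP 4.4).
- Randomized: 276 in a 2:1 ratio (SAP 4.1), so 184 and 92.
- M = 25 imputations (SAP 9.3).

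**Assumption.** The documents do not give the FMI, nor the DLQI variances and correlations from which to derive it. If 24% of Week 16 scores were missing and earlier visits told us nothing, FMI would be about 0.24. With visit correlations of 0.5 to 0.7 it simulates at about 0.19. The range shown is 0.05 to 0.30.

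**Step 1: reproduce the plan's figures.** With 140:70 and 0.70 v 0.50, power is 0.807 with the pooled null variance and 0.802 with the unpooled variance. At 170:85 the unpooled formula gives 0.872, as in protocol 9.3. Dropout: 276 x 0.76 = 209.8, against 210. The planning figures hold.

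**Step 2: expected z.** With complete data, SE = sqrt(0.25/92 + 0.21/184) = 0.0621, so z = 0.20/0.0621 = 3.22. With missing data, mu = 3.22 x sqrt(1 - FMI): 2.90 at FMI 0.19 and 2.81 at FMI 0.24.

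**Step 3: Monte Carlo SD of the pooled z.** s = sqrt(FMI/M). At M = 25, sqrt(0.19/25) = 0.087 and sqrt(0.24/25) = 0.098.

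**Step 4: probability that two seeds disagree.** Take z ~ N(mu, 1) and q = Phi((z - 1.96)/s), and average 2q(1 - q) over z. A close hand approximation is phi(mu - 1.96) x s x 2/sqrt(pi):

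- FMI 0.24: 0.279 x 0.098 x 1.128 = 0.031.
- FMI 0.19: 0.257 x 0.087 x 1.128 = 0.025.

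Numerical integration at the planned effect with 276 subjects gives the following disagreement rates:

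| FMI | mu | s at M=25 | M=25 | M=200 | M=500 |
|---|---|---|---|---|---|
| 0.05 | 3.14 | 0.045 | 1.01% | 0.36% | 0.22% |
| 0.10 | 3.05 | 0.063 | 1.56% | 0.55% | 0.35% |
| 0.19 | 2.90 | 0.087 | 2.53% | 0.89% | 0.57% |
| 0.24 | 2.81 | 0.098 | 3.08% | 1.09% | 0.69% |
| 0.30 | 2.69 | 0.110 | 3.76% | 1.33% | 0.84% |

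**Step 5: other effect sizes.** At the earlier-study rates in SAP 4.4 (0.83 v 0.50), complete-data z is 0.33/0.0590 = 5.59, and disagreement at M = 25 is 0.07% even at FMI 0.24. Under no effect it is 1.3% at FMI 0.24.

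**Step 6: spread of p at the boundary.** For a trial at z = 1.96, the 95% range over seeds is 1.96 +/- 1.96s.

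- M = 25: z 1.79 to 2.13, p 0.033 to 0.074 (FMI 0.19); z 1.77 to 2.15, p 0.031 to 0.077 (FMI 0.24).
- M = 500: p 0.046 to 0.055 (FMI 0.19) and 0.045 to 0.055 (FMI 0.24).

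**Step 7: simulation check.** DLQI at Weeks 0, 2, 4 and 16 was simulated with monotone dropout, predictive mean matching with K = 5, a stratified Mantel-Haenszel risk difference and Rubin's rules. Each of 1,500 trials per scenario was analysed with two independent sets of 25. With 276 subjects and 24% dropout, disagreement was 3.6%, 3.7% and 2.9% for visit correlations of 0, 0.5 and 0.7, each +/- about 0.9 points, with FMI 0.18 to 0.22. This is a little above the formula but of the same order. The simulated DLQI means, SDs and correlations are assumptions.

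**The case against.** The plan's choice can be defended on four grounds.

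**Validity is untouched.** Both seeds are fixed in advance, and PROC MIANALYZE applies Rubin's rules, which already allow for finite M. Relative efficiency, 1/(1 + FMI/M), is 0.992 at FMI 0.19 and 0.990 at FMI 0.24. A reader might infer that 25 imputations bias the estimate, inflate type I error or leave room to pick a favourable seed. The documents support none of these.

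**The data dominate.** A reader might also infer that near the threshold the verdict reflects the seed instead of the data. It does not: seed noise has variance FMI/M, or 0.008 to 0.010, against a sampling variance of about 1. It can tip only a trial whose z is already within about 0.2 of 1.96, and it tips in both directions.

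**Missingness may be lower than 24%.** That figure is an allowance for discontinuation. SAP 5.5 maps any assessment from Day 71 to the end of the Placebo-controlled Phase to Week 16 and includes discontinuation visits. Protocol Table 3 schedules the DLQI at early termination, and protocol 11.1 seeks that visit within 4 days of the last intake. Subjects who stop after Day 70 and attend therefore have an observed Week 16 score.

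**The effect may be larger than planned.** At the earlier-study rates the issue all but vanishes. The LOCF and NRI analyses in SAP 9.3 also involve no random draws, though they do not replace the primary p-value.

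All four points stand. They limit the size of the concern and rule out the stronger readings. They give no reason to keep the noise: a fixed seed makes a borderline verdict repeatable, but another seed could still reverse it.

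**Conclusion.** The point holds as a minor matter of precision. At the planned effect, with 276 subjects and FMI of 0.19 to 0.24, about 2.5 to 3 trials in 100 would change verdict on another seed. The rate is 1.0 to 1.6% at FMI 0.05 to 0.10 and below 0.1% at 0.83 v 0.50. The size rests on the assumed FMI and on the true effect being near 0.20. It is not an error in the plan, but an avoidable weakness in the p-value that gates all other claims.

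**What to change.** Before unblinding, replace 25 with 500 wherever it gives the number of imputed data sets in SAP 9.1, 9.3 and 9.4.1, including the text on combining results. Say plainly that 500 is the total: 500 data sets from the MCMC step, each completed once by predictive mean matching, or 500 directly from the latter if the pattern is already monotone. Keep both seeds, and state the sort order of the input data.

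Disagreement at the planned effect then falls to about 0.6 to 0.7%, roughly 4.5-fold (sqrt(500/25) = 4.47). With 200 data sets it would be about 0.9 to 1.1%. The imputation model and the test do not change. The cost is minutes of run time and larger intermediate data sets.

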8.3. Prohibited Concomitant Medications and Procedures

The following psoriasis medications cannot be administered for the duration of the study.

- Topical therapy
 - Topical therapy, unless otherwise specified in Section 8.1 (including, but not limited to topical corticosteroids, retinoids or Vitamin D analog preparations, tacrolimus, pimecrolimus, coal tar, anthralin/dithranol, or urea- and salicylic acid-containing moisturizers)
- Conventional systemic therapy
 - Conventional systemic therapy including but not limited to cyclosporine, methotrexate, retinoids, mycophenolate, thioguanine, hydroxyurea, sirolimus, sulfasalazine, azathioprine, fumaric acid esters, and corticosteroids
- Biologic agents, including:

- Adalimumab, etanercept, infliximab, or certolizumab pegol, ustekinumab, secukinumab, ixekizumab, brodalumab, guselkumab, tildrakizumab
- Phototherapy
 - Ultraviolet light B (UVB) or psoralens and long-wave ultraviolet radiation (PUVA)
- Use of any investigational drug or device
- Use of tanning booths, which may confound the ability to interpret data from the study.

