11. DISCONTINUATIONS

11.1. Treatment Discontinuation

The following events are considered sufficient reasons for discontinuing a subject from the investigational product(s):

- Adverse event
- Lack of efficacy
- Non-compliance with investigational products
- Withdrawal by subject
- Death
- Lost to follow-up
- Protocol deviation
- Pregnancy
- Physician decision
- Study terminated by sponsor
- Other (to be specified on the eCRF)

Subjects have the right to withdraw from the study at any time and for any reason. The reason for discontinuation should be recorded in the eCRF and in the source documents.

When a subject is discontinued from treatment, the Investigator should make every attempt possible to have the subject evaluated at the Early Termination Visit within 4 days of the last intake of investigational product.

The decision to discontinue a subject can be taken at any time and remains the responsibility of the treating physician, which will not be delayed or refused by the sponsor. However, prior to discontinuing a subject, the Investigator may contact the Medical Monitor or designee and forward appropriate supporting documents for review and discussion, without identifying the subject.

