5.3.2. Per-Protocol Population

The per-protocol (PP) population includes all subjects who are in the ITT population, who receive at least one dose of IP, have both baseline and at least one post-treatment DLQI evaluation, and have no major protocol deviations which may affect analyses in the Placebo-controlled Phase. The PP population is only used to supplement the primary endpoint ITT analysis.

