5.5. Time Points

Time points in all analyses are based on the visits/study weeks using the following visit mapping algorithm, which may or may not be the same as the visits/study weeks as recorded in the database.

Post baseline time points in all analyses will be captured based on analysis visit window (range of study days) around the target day for each analysis visit, based on the actual day of evaluation relative to a reference date. Appropriate dates will be used to calculate the study day, e.g., date of measurement or date of specimen collection will first be used, and then the date of visits/study weeks as recorded in the database will be used. If there are multiple measurements within a time point based on the study day, then the non-missing value from the closest measurement to the planned study day will be used for that visit. If the value at a scheduled visit is missing and there is no value available within the time window based on the study day, the value at the study week will be missing.

Table 2: Table for Visit Mapping for by Time Point Analysis

Analysis Visit	Target Day	Visit Window
Baseline	1	≤ 1
Placebo-controlled Phase (for all endpoints)		
Week 2	15	2 – 21
Week 4	29	22 – 70
Week 16	113	71 – End of Placebo-controlled Phase
Apremilast Extension Phase (for efficacy endpoints)		
Week 20	141	Start of Apremilast Extension Phase – 182
Week 32	225	183 – 294
Week 52	365	295 – End of Apremilast Extension Phase
Apremilast Extension Phase (for safety endpoints)		

Apremilast

Statistical Analysis Plan. Protocol CC-10004-PSOR-020

Amgen INC.

Week 20	141	Start of Apremilast Extension Phase – 182
Week 32	225	183 – 266
Week 44	309	267 – 337
Week 52	365	338 – End of Apremilast Extension Phase

Note: Target day and visit window are relative to the date of Visit 2/Week 0 (Day 1) for randomization. Definitions for baseline and start or end of the phases are specified in [Section 5.25.2](#) and [5.4](#) for both efficacy and safety analysis.

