9.4.1. Secondary Efficacy Endpoints in the Placebo-controlled Phase

All analyses will be conducted using ITT population including data from the Placebo-controlled Phase (Week 0 to Week 16). Table 5 is the summary on how the secondary efficacy endpoints at Week 16 will be analyzed.

Table 5 Analysis on the Secondary Efficacy Endpoints at Week 16

Summary Measure of Endpoint	Primary Analysis	Supportive Analysis
Mean change from baseline in DLQI at Week 16	ANCOVA model adjusted by baseline DLQI score, treatment, stratification factor on data with MI	ANCOVA model adjusted by baseline DLQI score, treatment, stratification factor on data with LOCF
Mean percent change in Body Surface Area (BSA) affected by psoriasis at Week 16	ANCOVA model adjusted by BSA score, treatment, stratification factor on data with MI	ANCOVA model adjusted by BSA score, treatment, stratification factor on data with LOCF
Mean change from baseline in Pruritus Numeric Rating Scale (NRS) score at Week 16	ANCOVA model adjusted by baseline NRS score, treatment, stratification factor on data with MI	ANCOVA model adjusted by baseline NRS score, treatment, stratification factor on data with LOCF
Mean change from baseline in skin discomfort/pain Visual Analog Scale (VAS) at Week 16	ANCOVA model adjusted by baseline VAS score, treatment, stratification factor on data with MI	ANCOVA model adjusted by baseline VAS score, treatment, stratification factor on data with LOCF
Proportion of subjects who achieve Psoriasis Area Severity Index (PASI) < 3 at Week 16	CMH test adjusting for the stratification factor on data with MI	CMH test adjusting for the stratification factor on data with LOCF and data with NRI
Proportion of subjects who achieve Patient Benefit Index (PBI) global score of ≥ 1 at Week 16	CMH test adjusting for the stratification factor on data with MI	CMH test adjusting for the stratification factor on data with LOCF and data with NRI
Mean percent change from baseline in European Quality of	ANCOVA model adjusted by baseline EQ-5D score*, treatment,	ANCOVA model adjusted by baseline EQ-5D score*, treatment,

Apremilast

Statistical Analysis Plan. Protocol CC-10004-PSOR-020

Amgen INC.

Life 5-Dimension (EQ-5D) score* at Week 16	stratification factor on data collected on scheduled Week 16 visit	stratification factor on end of phase assessment

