9.4.2. Secondary Efficacy Endpoints in the Apremilast Extension Phase

The analyses will be conducted using the ITT population for subjects who entered the Apremilast Extension Phase. For binary endpoints, frequency tables will be provided by time point based on data with NRI. For continuous endpoints, summary statistics will be provided by time point (including end of phase assessment) on DAO.

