9.6. Analyses of Exploratory Efficacy Endpoints

For exploratory efficacy endpoints, descriptive summary statistics or proportion of subjects achieving pre-specified criteria will be summarized by treatment arm by time points.

9.6.2. Manifestation specific clinical endpoints at Week 16, Week 32, and Week 52

The following is the list of manifestation specific endpoints according to the pre-specified treatment improvement criteria.

- Achieving Static Physician Global Assessment (sPGA) score of 0 or 1 (among subjects randomized to the strata with moderate to severe psoriasis in visible areas, defined as sPGA \geq 3 at baseline, which include the dorsal hand, face, neck, or hairline) at Weeks 16, 32, 52
- Achieving Scalp Physician Global Assessment (ScPGA) score of 0 or 1 (among subjects randomized to the strata with moderate to severe scalp psoriasis, ScPGA \geq 3 at baseline) at Weeks 16, 32, 52

Apremilast

Statistical Analysis Plan. Protocol CC-10004-PSOR-020

Amgen INC.

- Achieving Nail Psoriasis Severity Index (NAPSI) score of 0 in the target fingernail (among subjects randomized to the strata with presence of nail psoriasis, defined as onycholysis and onychodystrophy in at least 2 fingernails at baseline) at Weeks 16, 32, 52
- Achieving Static Physician Global Assessment-Genitalia (sPGA-G) score of 0 or 1 (among subjects randomized to the strata with moderate to severe genital psoriasis, sPGA-G ≥ 3 at baseline) at Weeks 16, 32, 52
- Achieving Palmoplantar Psoriasis Physician Global Assessment (PPPGA) score of 0 or 1 (among subjects randomized to the strata with moderate to severe palmoplantar psoriasis, PPPGA ≥ 3 at baseline) at Weeks 16, 32, 52

The number and percentage of subjects with improvement among the subgroup of subjects demonstrating the corresponding manifestation at baseline by time point (including all visits with scheduled assessments and end of phase assessment) will be summarized based on data with NRI (including end of phase assessment). Shift tables for each of the manifestation assessment shift from baseline to post-baseline visits and end of phase assessment in all subjects will be provided based on DAO. The new onset on subject without such manifestations at baseline will also be assessed using shift tables.

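### Responder rates at Weeks 32 and 52 count responses recorded after prohibited psoriasis therapy as apremilast responses

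*SAP*

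**What the plan says.** - **Prohibited therapy.** Protocol 8.3 introduces its list with "The following psoriasis medications cannot be administered for the duration of the study". The list covers topical, conventional systemic, biologic and light therapy. It does not say what happens to a subject, or to later data, if one is used.
- **Consequence of a deviation.** Protocol 11.1 includes protocol deviation and lack of efficacy in a list headed "The following events are considered sufficient reasons for discontinuing a subject from the investigational product(s". Stopping is allowed but not stated as mandatory.
- **Meaning of NRI.** The only description is in SAP 9.3, for a supportive analysis of the primary endpoint: "ITT population treating missing values using the non-responder imputation (NRI) method".
- **Use of NRI after Week 16.** SAP 9.4.2 states "For binary endpoints, frequency tables will be provided by time point based on data with NRI". This covers DLQI response, PASI below 3 and PBI of at least 1. SAP 9.6.2 also uses NRI for the five manifestation-specific response endpoints.
- **Meaning of missing.** Under SAP 5.5 a visit value is missing when the scheduled value is absent and "there is no value available within the time window based on the study day". Therapy use plays no part.
- **Per-protocol set.** SAP 5.3.2 excludes major deviations that may affect the Placebo-controlled Phase, and adds: "The PP population is only used to supplement the primary endpoint ITT analysis".
- **Tables of use.** SAP 7 summarises deviations by arm for both phases and lists them by subject. SAP 8.5.4 tabulates concomitant medications, including for the Apremilast Exposure Period. Neither is tied to response.

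**The concern.** Protocol Section 2 makes the long-term effect of apremilast 30 mg BID at Weeks 32 and 52 a secondary objective. The responder rates at those visits have no comparator, because SAP 9.1 plans only within-arm estimates after Week 16, with plots meant to show whether benefit is sustained. A reader will take each rate as what apremilast achieves. If some responders had added a topical corticosteroid, a biologic or phototherapy, the rate describes apremilast plus that therapy, and no planned table shows how many such responders there are. Any error in attribution favours the product.

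PASI below 3 is especially exposed. Inclusion criterion 5 admits a baseline PASI from 3 to 10, so a subject entering near 3 needs only a small improvement to count as a responder.

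**Working it through.** **Step 1: follow one subject through the rules.** A subject in the extension starts a prohibited therapy for psoriasis and attends Week 52.

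1. Protocol 8.3 and 11.1 do not require withdrawal, so the subject may stay in the study.
2. A value exists in the Week 52 window, so under SAP 5.5 it is not missing.
3. NRI acts on missing values only, so the value stands. If it meets the criterion, SAP 9.4.2 or 9.6.2 counts a responder.
4. The per-protocol set does not apply after Week 16.

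Withdrawal does not always change this. The extension phase ends on the day of the discontinuation visit (SAP 5.2.2), and the efficacy window for Week 52 runs from Day 295 to the end of the phase (SAP 5.5, Table 2). An early-termination value from Day 295 onward is therefore used as Week 52. Only a subject with no value in the window becomes a non-responder.

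**Step 2: size.** The plan gives no figure to reproduce here. Inputs:

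- *u*: share of subjects in the denominator who use such therapy. Not in the documents; assumed 5–10%.
- *p*: share of users who would have responded anyway. Illustrative value 0.70, the Week 16 planning rate for apremilast in SAP 4.4 (0.50 + 0.20). No rate is given for Weeks 32 or 52.
- *c*: share of the remaining users who respond because of the added therapy. Assumed.

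Formulas:

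- Share of users recorded as responders: q = p + (1 − p) × c.
- Fall in the reported rate if users are scored as non-responders: u × q.
- Part of the reported rate owed to the added therapy itself: u × (1 − p) × c.

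Ceiling (p = 0, c = 1): both quantities equal u, that is 5 to 10 points. SAP 4.1 plans 276 subjects at 2:1, so 276 × 2/3 = 184 on apremilast. If all entered the extension, the ceiling is 184 × 0.05 = 9.2 to 184 × 0.10 = 18.4 subjects.

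Illustration (p = 0.70, c = 0.5):

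- q = 0.70 + 0.30 × 0.5 = 0.85.
- Fall under the rule: 0.05 × 0.85 = 4.25 points to 0.10 × 0.85 = 8.5 points.
- Owed to the added therapy: 0.05 × 0.30 × 0.5 = 0.75 points to 0.10 × 0.30 × 0.5 = 1.5 points.
- The rest, 0.05 × 0.70 = 3.5 to 0.10 × 0.70 = 7.0 points, is users who would have responded anyway.

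**Step 3: does the same change belong at Week 16?** SAP 4.4 states power 0.807 for 0.70 against 0.50 with 140 and 70 subjects. Unpooled: SE = √(0.50 × 0.50/70 + 0.70 × 0.30/140) = 0.0712, and Φ(0.20/0.0712 − 1.96) = 0.802. The pooled formula gives 0.807, so the figure reproduces.

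Now assume that 10% of placebo subjects and no apremilast subjects use prohibited therapy, and that half of the would-be non-responders among them convert:

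| | Placebo rate | Difference from 0.70 |
|---|---|---|
| No therapy effect | 0.50 | 0.20 |
| As recorded | 0.50 + 0.10 × 0.50 × 0.5 = 0.525 | 0.175 |
| All users scored non-responders | 0.90 × 0.50 = 0.45 | 0.25 |

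On these assumptions, recording understates the difference by 0.025 and the rule overstates it by 0.05.

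**The case against.** The strongest reply is that keeping observed values whatever the deviation is an ordinary intention-to-treat choice. No test is affected after Week 16, and the size is conjecture. Prohibited use will also be visible in the deviation and medication tables, and a subject who is withdrawn and has no later value is already a non-responder. A rule that scores every user as a non-responder has its own fault: one brief topical use soon after Week 16 would make a subject a Week 52 non-responder. Read literally, Protocol 8.3 also lists tanning booths and investigational drugs or devices.

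Much of this stands. The choice is defensible for a rate that describes subjects regardless of added therapy, and the documents do not fix the size. The trigger must therefore be narrow, and the unadjusted rate should stay on view. What does not stand is that the tables suffice: they count users, and do not show how many responders were users.

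A reader might also infer that the Week 16 comparison is diluted and loses power. With 15% use on placebo only and half of would-be non-responders converting, the placebo rate is 0.50 + 0.15 × 0.50 × 0.5 = 0.5375, and unpooled power falls from 0.802 to 0.628. The documents do not support making that part of this point. They give no usage rate in either arm, so heavier use on placebo is an assumption. The powered test is the multiple-imputation analysis in SAP 9.3, which a change to NRI would leave untouched. For the binary secondary endpoints NRI is likewise only supportive (SAP Table 5: "CMH test adjusting for the stratification factor on data with LOCF and data with NRI").

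**Conclusion.** The point holds for Weeks 32 and 52. As written, the only planned responder analysis at those visits counts a response after prohibited psoriasis therapy as a response to apremilast, and no planned output separates the two. This follows from the text and needs no assumption about frequency.

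The size does need one. At 5–10% use the ceiling is 5–10 points, reached only if every user is recorded as a responder and none would have responded otherwise. In the illustration above, the part owed to the added therapy is about 1 point.

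The point does not extend to Week 16. Scoring users as non-responders there changes the question being asked, and with heavier use on placebo it would inflate the treatment difference. It would not restore the power of the primary test. This is an inexpensive improvement to descriptive long-term results, and the primary conclusion does not depend on it.

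**What to change.** In SAP 9.4.2 and 9.6.2, for Weeks 32 and 52, define non-response as a value that is either:

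- missing; or
- assessed on or after first use, in the extension phase, of a topical, conventional systemic, biologic or light therapy listed in Protocol 8.3 and recorded with psoriasis as the indication.

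Identify use from the concomitant-medication eCRF, by a review that does not look at response. Next to each rate, report the number of such users and the rate without this rule. Leave the primary multiple-imputation analysis and the Week 16 NRI data sets unchanged.

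The cost is SAP wording, one flag and the review. Protocol 8.1 already requires indication and start and stop dates on the eCRF. The long-term rates become somewhat less favourable, and a user who would have responded anyway is scored as a non-responder, which is why both rates should be shown. The change concerns analysis only and alters nothing in how subjects are managed.
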